APPENDIX G. FACT/GOG-NEUROTOXICITY QUESTIONNAIRE, VERSION 4.0

(Cella 1993)

By circling one (1) number per line, please indicate how true each statement has been for you during the past 7 days.

ADDITIONAL CONCERNS	Not at all	A little bit	Some- what	Quite a bit	Very much
I have numbness or tingling in my hands	0	1	2	3	4
I have numbness or tingling in my feet	0	1	2	3	4
I feel discomfort in my hands	0	1	2	3	4
I feel discomfort in my feet	0	1	2	3	4
I have joint pain or muscle cramps	0	1	2	3	4
I feel weak all over	0	1	2	3	4
I have trouble hearing	0	1	2	3	4
I get a ringing or buzzing in my ears	0	1	2	3	4
I have trouble buttoning buttons	0	1	2	3	4
I have trouble feeling the shape of small objects when they are in my hand	0	1	2	3	4
I have trouble walking	0	1	2	3	4

PR	Partial Response/remission
Q3W	Administration every 3 weeks
RP2D	Recommended Phase 2 Dose
SAE	Serious Adverse Event
SAP	Statistical Analysis Plan
SD	Stable Disease
$t_{1/2}$	Terminal half life
TBL	Total Bilirubin
TEAE	Treatment-emergent adverse event
T_{max}	Time at which C_{max} occurs
TPP	Time-to-Progression
TTR	Time to Response
ULN	Upper Limit of Normal
Vss	Volume of distribution at steady state
WHO Drug	World Health Organization drug dictionary

1. INTRODUCTION

1.1. Background

IMGN853 0401 is an open label, non-randomized, first-in-human (FIH), dose-escalation and dose-expansion Phase 1 study. It is designed to identify the maximum tolerated dose (MTD) of IMGN853 when administered intravenously as a single agent in adult patients with relapsed or refractory epithelial ovarian cancer (EOC) and other FOLR1-positive solid tumors (dose escalation) and enable further evaluation of the recommended Phase 2 dose (RP2D). The safety, tolerability, pharmacokinetics (PK), pharmacodynamics (Pd), immunogenicity, and preliminary anti-tumor activity of IMGN853 will be characterized.

During dose escalation two dosing schedules were evaluated: Schedule A (IMGN853 administered on Day 1, with cycles repeating every 21 days (Q3W)) and Schedule B (IMGN853 administered on Days 1, 8, and 15, with cycles repeating every 28 days). Dose expansion began once the Schedule A MTD was identified and a dose was selected for further exploration. Schedule B evaluation was stopped prior to identifying the MTD

The purpose of this Statistical Analysis Plan (SAP) is to outline the statistical principles which will be used to analyze and present the data from this study. This SAP includes a description of the study endpoints, stopping rules, and analysis populations. Table, Figure, and Listing shells will be supplied in a separate document. The SAP may be modified until the time of data base lock. Any deviations from the SAP, including any deviations after the time of database lock, will be documented in the study report.

The protocol for IMGN853 0401 describes the general approach to analysis of data from the study. This Statistical Analysis Plan is based on [Amendment 10](#) of Clinical Study Protocol IMGN853 0401. A brief history of the protocol amendments is presented in Table 1.

Table 1: History of Protocol and Amendments to the Protocol

Version	Approval Date	Changes Expected to Impact the SAP
Protocol	01Mar2012	
Amendment 1	13Apr2012	Lowered starting dose, added additional escalation cohort
Amendment 2	18Oct2012	Endometrioid endometrial cancer was added to the list of tumors that could be enrolled without proof of FOLR1+.
Amendment 3	07Mar2013	Secondary endpoints PFS, TTP, and DoR added.
Amendment 4	13May2013	Assay for Circulating Tumor Cells (CTCs) and other Pd assessments added
Amendment 5	18Oct2013	FLT-PET was removed from the protocol Additional expansion cohort added for patients with endometrial cancer. Dosing procedure modified to employ adjusted ideal body weight. Collection of CTCs in selected patients added.

Table 1: History of Protocol and Amendments to the Protocol (Continued)

Version	Approval Date	Changes Expected to Impact the SAP
Amendment 6	27Nov2013	Additional dosing schedule added (Schedule B). Pd/Biomarker studies revised. Increased number of patients. Data capture of Ocular symptom assessments separated from Ophthalmic exams.
Amendment 7	13Aug2014	Estimated number of patients has been increased. Size of MTD expansion cohorts was revised. Circulating Tumor Cell analyses have been removed from the study. Assessment of objective response rate for expansion cohorts has been added to the protocol.
Amendment 8	26Aug2014	None
Amendment 9	25Feb2015	Updated exploratory objectives and endpoints. Updated the number of patients to be enrolled in Dose Expansion Cohort 1. Estimated number of patients planned therefore has increased. Added language to allow for selection of a less frequent dosing regimen for Schedule B if dosing is deemed sub-optimal. Removed requirement for confirmation of the objective responses. Use of lubricating eye drops made mandatory. Increased requirements for eye exams.
Amendment 10	02Sep2015	Schedule B dosing discontinued. A total of five specific dose expansion cohorts were defined: Cohort 1:Platinum resistant EOC Cohort 2:Advanced or recurrent uterine cancer Cohort 3: Relapsed ovarian cancer amendable to biopsy Cohort 4: Relapsed/refractory NSCLC adenocarcinoma or BAC Cohort 5: Relapsed EOC, using corticosteroid eye drops

2. STUDY DESIGN

2.1. Protocol Objectives

All objectives apply to both dosing schedules and all cohorts unless otherwise noted.

2.1.1. Primary

- Determine MTD and RP2D of IMGN853 when administered intravenously

2.1.2. Secondary

- Evaluate the safety and tolerability of IMGN853
- Evaluate the effectiveness of primary, prophylactic steroid eye drops in preventing or lessening keratopathy and/or blurred vision
- Characterize the PK of IMGN853 when administered intravenously
- Describe any preliminary evidence of IMGN853 antitumor activity
- Characterize the immunogenicity of IMGN853

2.1.3. Exploratory

- Determine the predictive value of FOLR1 expression on tumor cells as a biomarker for IMGN853 anti-tumor activity
- Explore the association of molecular alterations in oncogenic genes and pathways, and established molecular tumor subtypes (e.g. the four molecular subtypes of high grade serous ovarian cancer) with FOLR1 expression and IMGN853 antitumor activity
- Evaluate any additional tumor or blood based biomarkers that may be associated with sensitivity or resistance to IMGN853 (e.g. MDR1 expression, polymorphism)
- MTD Expansion Cohort#3 only: Characterization of post-dose biopsy samples to evaluate:
 - Presence of IMGN853 in tumor
 - Pd activity measured as changes in Ki67 from baseline, and/or other biomarkers based on emerging data
 - Changes in FOLR1 expression post-treatment and disease progression
 - Changes in the numbers of tumor infiltrating immune cells after treatment with IMGN853
 - Mechanism of relapse or treatment emerging resistance to IMGN853

2.2. Study Endpoints

2.2.1. Primary

The primary endpoints:

- MTD
- RP2D.

2.2.2. Secondary

Secondary endpoints include:

- Treatment-emergent adverse events (TEAEs) and clinically significant \geq Grade 3 changes in laboratory test results, physical examination, ECGs or vital signs
- Treatment-emergent ocular adverse events
- PK parameters: C_{max} , AUC, terminal half-life ($t_{1/2}$), clearance (Cl), volume of distribution at steady state (Vss), T_{max} , AUC
- Number of patients with RECIST 1.1 criteria (see [Protocol Appendix E](#)) clinical responses and/or number of patients with GCIG Cancer Antigen 125 (CA-125) criteria clinical responses (see [Protocol Appendix F](#))
 - Objective response rate (ORR; MTD Expansion Cohorts # 1 and 2)
 - Duration of response (DOR)
 - Progression-free survival (PFS)
 - Time-to-progression (TTP)
- Human Anti-Drug Antibody (HADA) and Human Anti-Human Antibody (HAHA) levels

2.2.3. Exploratory

Exploratory endpoints include:

- Evaluate FOLR1 expression by immunohistochemistry (IHC) (protein), qRT-PCR (mRNA) or other quantitative methods
- Establish mutational status, copy number alterations, and gene structure rearrangements in known oncogenic genes and pathways (e.g. mutations in p53, BRCA1/2 in ovarian cancer, PTEN/PIK3CA in endometrial cancer, EGFR, KRAS in NSCLC)
- Infer somatic/germline status of BRCA1/2 mutations using data generated from tumor tissue
- Analyze mRNA and/or protein expression of genes known to be over expressed or silenced in cancer, as well as genes associated with molecular cancer subtypes
- Evaluate expression and polymorphism of drug transporters such as MDR1 (i.e. P-glycoprotein (PgP))
- Evaluate additional biomarkers identified in preclinical studies that may be associated with IMGN853 sensitivity or resistance
- MTD Expansion Cohort #3 Only:
 - Measure binding of IMGN853 to tumor cells in post-treatment biopsy by anti-Maytansine IHC
 - Compare the number of Ki-67 positive cells in baseline biopsies with that of post-treatment biopsies using IHC

- Compare FOLR1 expression in archival samples, baseline, and post-treatment (Cycle 2 Day 8) biopsies by IHC
- Compare the number of different types of immune cells in baseline biopsies with that of post-treatment biopsies using IHC for cell-type specific markers
- Compare FOLR1 expression and mutation status at baseline with those of biopsies taken after relapse

2.3. Study Overview

IMGN853 0401 is an open label, non-randomized, FIH, dose-escalation and dose-expansion Phase 1 study. It is designed to identify the MTD of IMGN853 when administered intravenously as a single agent in adult patients with relapsed or refractory EOC and other FOLR1-positive solid tumors (dose escalation) and enable the selection and further evaluation of a RP2D (dose escalation and dose expansion). The safety, tolerability, PK, Pd, immunogenicity, and preliminary anti-tumor activity of IMGN853 will be characterized.

2.3.1. Dose Escalation

During dose escalation, 2 dosing schedules (Schedule A and Schedule B) were evaluated. Initially patients received IMGN853 using Schedule A. After the introduction of Schedule B ([Protocol Amendment 6](#)) patients received IMGN853 either using Schedule A or Schedule B. Following the enrollment of 4 of the Schedule B dose escalation cohorts, Schedule B escalation was closed ([Protocol Amendment 10](#)).

2.3.1.1. Schedule A

IMGN853 dosed on Day 1 of a 21-day cycle.

The first 4 escalation cohorts were single patient cohorts. Subsequent escalation cohorts used a standard 3+3 design, with each cohort consisting of 3 or 4 to 6 patients. The initial planned doses for Schedule A dose escalation are shown in Table 2, exploration of intermediate doses was allowed following CRC review of all available data.

Patients initially had their doses calculated based on their actual body weight, from [Protocol Amendment 5](#) onwards patients have had their doses calculated based on their adjusted ideal body weight (AIBW). When the MTD for Schedule A was identified and a RP2D selected for further evaluation, enrollment into the Expansion Cohorts began.

Table 2: Initial Planned Dose Levels for Schedule A

Dose Level	Dose (mg/kg) ^a	Percent Increase From Previous Dose Level	Number of Patients (Planned)
1	0.15	N/A1/20 HNSTD	1
2	0.5	233%	1
3	1.0	100%	1
4	2.0	100%	1
5	3.3	65%	3 or 4-6

Table 2: Initial Planned Dose Levels for Schedule A (Continued)

Dose Level	Dose (mg/kg) ^a	Percent Increase From Previous Dose Level	Number of Patients (Planned)
6	5.0	52%	3 or 4-6
7	7.0	40%	3 or 4-6
8	9.0	28%	3 or 4-6

^a Patients enrolled under [Amendment 5](#) or later were dosed based on AIBW. Patients enrolled prior to Amendment 5 were dosed based on actual body weight.

2.3.1.2. Schedule B

IMGN853 administered on Days 1, 8, and 15, with cycles repeating every 28 days.

The starting dose of IMGN853 for Schedule B was 1.1 mg/kg, which was 1/3 the 3.3 mg/kg dose level deemed clinically safe in 9 patients dosed at that level in Schedule A. All patient doses were calculated according to AIBW. Patients were enrolled in cohorts of 3 to 6 patients.

The initial planned doses for Schedule B dose escalation are shown in Table 3. If additional dose exploration was required to define the MTD then dose escalation could proceed at increments $\leq 25\%$. The CRC determined the magnitude of the dose escalation increments following review of available clinical and PK data from patients treated in the current cohort.

Table 3: Initial Planned Dose Levels for Schedule B

Dose Level	Dose (mg/kg) ^a	Percent Increase From Previous Dose Level	Number of Patients (Planned)
1	1.1	N/A	3 or 4-6
2	1.8	65%	3 or 4-6
3	2.5	40%	3 or 4-6
4	3.3	32%	3 or 4-6

^a Patients were dosed based on AIBW

2.3.2. Study Population

2.3.2.1. Dose Escalation

Patients with a pathologically documented, definitively diagnosed, advanced solid tumor that is either refractory to standard treatment, or for which no standard treatment is available, or the patient refuses standard therapy.

Enrollment without prior documentation of tumor FOLR1 expression was limited to a set of histologic subtypes which were likely to have a high incidence of FOLR1 positivity, as described in [Section 3.1.A](#) of the protocol.

2.3.2.2. Dose Expansion

Patients were enrolled into 1 of the following 5 expansion cohorts:

- Cohort 1 -patients with platinum-resistant EOC
- Cohort 2 - patients with advanced or recurrent uterine cancer
- Cohort 3 - patients with relapsed or refractory EOC
- Cohort 4 - patients with relapsed/refractory non-small cell lung cancer (NSCLC) adenocarcinoma or bronchioloalveolar carcinoma (BAC)
- Cohort 5 - patients with EOC which has relapsed following platinum-based therapy and who will receive prophylactic corticosteroid eye drops

Further details for the Criteria for Selection of Patient Population are described in [Section 3.1](#) of the protocol.

2.3.2.3. Enrollment

Patients who received at least one dose of IMGN853 will be considered enrolled. Patients who were issued a patient number, but who did not successfully complete the screening process and who did not receive a dose of IMGN853 will be considered screen failures. Patient numbers were not re-issued.

2.3.3. Sample Size

Approximately 209 patients were to be enrolled in the study, allowing for dropouts and expansion of dose escalation cohorts as needed.

2.3.3.1. Dose Escalation

Ascending doses of IMGN853 were evaluated to identify the MTD for both dosing schedules. In Schedule A, single patient was enrolled into the first 4 cohorts and then 3 or 4 to 6 patients into the following cohorts dependent on the incidence of DLTs and all other emerging data. In Schedule B, 3, or 4 to 6 patients were enrolled into each of the cohorts dependent on the incidence of DLTs and all other emerging data. The actual number of patients accrued during this phase was determined by the evaluation of all patient data.

2.3.3.2. Dose Expansion

Following identification of the MTD for Schedule A and the selection of a dose for further evaluation there was an expansion phase. The number of patients to be enrolled into each of the expansion cohorts were:

- Cohort 1 - 40 patients
- Cohort 2 - 20 patients
- Cohort 3 - 20 patients
- Cohort 4 - 20 patients
- Cohort 5 - 40 patients

If the true DLT rate at the MTD is 10-20%, there is a 98.5-99.9% probability of observing at least one DLT in each 40 patient cohort. If the true response rate at the MTD is 20%, there is a 99.9% probability of observing at least one response in each 40 patient cohort ([Table 4](#)).

Table 4: Probability of Observing $\geq X$ Events (Response or DLT) for a 40 Patient Cohort

X (Number Observed)	True Event Rate		
	10%	20%	30%
1	0.985	0.999	0.999
2	0.919	0.998	0.999
3	0.777	0.992	0.999
4	0.577	0.972	0.999
5	0.371	0.924	0.997
6	0.206	0.838	0.991

2.3.4. Treatment Randomization

No randomization will be performed in this study.

2.3.5. Schedule of Assessments

See [Protocol Appendix A](#) and [Appendix B](#).

2.4. Interventions

2.4.1. Clinical Trial Material

2.4.1.1. Schedule A

Patients will receive an infusion of IMGN853 as a single agent on Day 1 of a planned 21 day cycle. For logistical reasons such as holidays, delays in the scheduled study treatment of up to 3 days may be allowed. Additionally, shifts in the start of a new cycle by -1 or +3 days will be permitted in Cycles ≥ 3 .

2.4.1.2. Schedule B

Patients received infusions of IMGN853 as a single agent on Days 1, 8, and 15 of each planned 28-day cycle. A delay of 1 day in the doses received on Days 8 and 15 was permitted; if a delay occurred, each subsequent dose in that cycle was shifted by 1 day. Intervals of < 7 days between each dose were not permitted. The start of the next cycle remained the same.

2.5. Study Procedures

Secondary and exploratory objectives include characterization of PK, Pd, immunogenicity, FOLR1 levels, and other potential biomarkers in blood, tumor tissue, and biologic fluids that might predict response to IMGN853. Full profiles of blood samples for PK measurements were taken in Cycles 1 and 3 for all patients. Additionally, a single sample was collected pre-dose and following completion of the infusion in Cycles 2, 4, 5 and 6 for PK. A single blood sample for analysis of HADA and HAHA was taken on Day 1 of Cycles 2, 4, and 5

and at EOT and 28 day follow up visits, and three hours and 1 week following the onset of an IMGN853 infusion-related reaction. If PK sampling were performed concurrently, the HADA and HAHA samples were taken from the PK sample tube.

Ki67 IHC staining was assessed as a marker of cell proliferation on fresh biopsy samples from patients in Expansion Cohort 3.

All patients were genotyped for Fc γ R alleles via Peripheral Blood Mononuclear Cell (PBMC) analysis at screening.

Samples for Fc γ R were taken at screening. P-glycoprotein (PgP) IHC staining will be assessed in archived tumor tissues and on fresh biopsy samples obtained from patients in the expansion cohorts.

FOLR1 expression via a homocysteine-dependent upregulation of FOLR1 mRNA translation and plasma total homocysteine levels will be assessed in all patients at baseline, during Cycle 2, and at the end of treatment visit. Plasma methylmalonic acid (MMA) will be analyzed in parallel with plasma total homocysteine to differentiate folate and B12 status.

Exploratory biomarkers were collected pre-dose on the first day of each cycle and at other noted time points. Details can be found in [Sections 6](#) and [Section 7](#) of the study protocol.

3. GENERAL ANALYTICAL CONSIDERATIONS

3.1. Data Sources

All data is to be collected via eCRFs through remote data entry, or through electronic transfers. [Section 13](#) of the study protocol provides additional details regarding data recording and handling.

3.2. Definition of Baseline

Cycle 1, Day 1 (Study Day 1) was designated as the first day a patient receives IMGN853. For most measurements, baseline labs were taken pre-dose on Day 1. If pre-dose assessments on Day 1 are not available, the screening result closest to (prior to dosing on) Day 1 will be substituted.

3.3. Missing Data

TEAE onset dates will be reported in listings as collected. Every effort will be made to query missing dates. If exploratory analyses require imputed dates, the following procedure will be employed:

- TEAE onset dates with missing year will be assumed to occur on Study Day 1.
- TEAE dates with missing month will be assumed to occur on the first day of the non-missing year, except for TEAEs occurring in the first year of dosing, in which case the date will be the first day of dosing.

- TEAE dates with non-missing month and missing day will be assumed to occur on the first day of the non-missing month, except for TEAEs occurring in the first month of dosing, in which case the date will be the first day of dosing.

All other data will be reported as they are collected. No imputation methods will be used to replace missing data.

3.4. Outliers

No adjustments for outliers will be made.

3.5. Multiple Study Centers

No adjustment for stratification by the study centers is planned.

3.6. Interim Analyses or Timing of Analyses

No formal interim analysis is planned for this study. However, a review of safety data and available preliminary PK data will be conducted by the CRC after the MTD or a RP2D for IMGN853 has been determined.

3.7. Analysis Populations

Three analysis populations will be defined for use with various analyses. The following table illustrates the relationship between each population and the analyses for which the data from the population will be used (Table 5).

Table 5: Analysis Populations

Analysis Population	Analysis				
	Baseline	Patient Disposition	Efficacy	Safety	DLT
Safety	X	X		X	X
Response-Evaluable			X		
CA-125-Evaluable			CA-125 only		

3.7.1. Safety Population

The Safety Population will consist of all patients who received at least one dose of study drug.

3.7.2. Response-Evaluable Population

To meet the definition of response-evaluable, patients must have
EITHER:

- received a radiographic assessment at baseline,
- received at least one dose of IMGN853, and

- have had at least one post-dose tumor assessment;

OR

- have died within 105 days of receiving their first dose, or
- have clinically progressed within 105 days of receiving their first dose.

3.7.3. CA-125 Evaluable Population

To meet the definition of CA-125 evaluable, patients must have a baseline CA-125 value $\geq 2\times$ ULN, received at least one dose of IMGN853, and must have had at least one post-dose CA-125 assessment. This population will be used in CA-125 response analysis only.

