2.4. Secondary Endpoints

- Treatment-emergent adverse events and clinically significant ≥ Grade 3 changes in laboratory test results, physical examination, ECGs or vital signs
- Treatment-emergent ocular adverse events
- PK parameters: C_{max}, AUC, terminal half-life (t_{1/2}), clearance (Cl), volume of distribution at steady state (V_{ss}), T_{max}, AUC
- Number of patients with RECIST 1.1 criteria (Appendix E) clinical responses and/or number of patients with GCIG CA-125 criteria clinical responses (Appendix F)
 - Objective response rate (ORR; MTD Expansion Cohorts # 1 and 2)
 - Duration of response (DOR)
 - Progression-free survival (PFS)
 - Time to progression (TTP)
- Human-Anti-Human Antibody (HAHA) and Human-Anti-Drug Antibody (HADA) levels

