APPENDIX F. GYNECOLOGIC CANCER INTERGROUP (GCIG CRITERIA FOR EVALUATION OF CA-125

(Rustin 2004)

On the basis of the available data and extensive discussions among the cooperative groups within the GCIG, it is recommended that the following definition of response be used in ovarian cancer trials so that response can be measured by either RECIST or CA 125 criteria. If the response is evaluable by both criteria, then the date of response will be the date of the earlier of the two events.

Definition of response:

≥ 50% reduction in CA 125 levels from baseline

- the response must be confirmed and maintained for at least 28 days
- the pretreatment sample must be ≥ 2.0 times the UNL and within 2 weeks prior to starting treatment
- the date of response corresponds to the date when the CA 125 level is first reduced by 50%

To calculate CA 125 responses accurately, the following rules apply:

- 1) Intervening samples and the 28-day confirmatory sample must be less than or equal to (within an assay variability of 10%) the previous sample
- 2) Variations within the normal range of CA 125 levels will not interfere with the response definition.

Timing of CA125 assessments:

The Gynecologic Cancer Intergroup (GCIG) recommends that CA 125 measurements be taken at specific time intervals.

- The first sample would be collected within 2 weeks before treatment is started
- Later samples would be collected at intervals of 2–4 weeks during treatment and at intervals of every two or three months during follow-up.
- For each patient, the same assay method must be used and the assay must be tested in a quality-control scheme. Patients are not evaluable by CA 125 if they have received mouse antibodies or if there has been medical and/or surgical interference with their peritoneum or pleura during the previous 28 days.

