This CA 125 response definition has been produced to evaluate relapse therapy. If assessing therapy that includes two treatment modalities for relapse (e.g., surgery and chemotherapy), any CA 125 response results from both treatments. CA 125 cannot distinguish between the effects of each treatment. To calculate response rates in protocols, an intent-to-treat analysis should be used that includes all patients with an initial CA 125 level of at least twice the upper limit of normal as eligible and evaluable. In addition to calculating response rates in protocols, it is advisable to record those patients who have both a CA 125 response and whose CA 125 level falls to within the normal range.

ImmunoGen, Inc. Confidential Page 137 of 138

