5.1.7. CA-125 Response

A CA-125 response is defined as a $\geq 50\%$ reduction in CA-125 levels from baseline. The response must be confirmed and maintained for at least 28 days. The baseline sample must be ≥ 2.0 times the upper limit of normal (ULN) and within two weeks prior to starting treatment. The date of response corresponds to the date when the CA-125 level is first reduced by 50%. The summary table for CA-125 will be based on CA-125 evaluable population for the expansion cohorts only.

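### The CA-125 response percentage leaves out patients with no post-dose sample, contrary to the intent-to-treat denominator in protocol Appendix F

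*SAP*

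**What the plan says.** Protocol 2.4 lists among the secondary endpoints the "number of patients with GCIG CA-125 criteria clinical responses (Appendix F"). SAP 2.2.2 repeats this and also points to Appendix F.

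For calculating response rates, Appendix F says that "an intent-to-treat analysis should be used that includes all patients with an initial CA 125 level of at least twice the upper limit of normal". Every such patient counts as evaluable, and there is no condition on later samples. Elsewhere, the same appendix makes patients non-evaluable by CA-125 "if there has been medical and/or surgical interference with their peritoneum or pleura during the previous 28 days".

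SAP 3.7.3 defines the CA-125 evaluable population by three conditions: a baseline of at least twice ULN, and having "received at least one dose of IMGN853, and must have had at least one post-dose CA-125 assessment". SAP 5.1.7 then states: "The summary table for CA-125 will be based on CA-125 evaluable population for the expansion cohorts only". That section carries over Appendix F's 50% fall, 28-day confirmation, baseline threshold and two-week baseline window. It does not carry over the interference rule. The SAP gives no reason for either difference.

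**The concern.** The post-dose condition selects patients on something that happens after treatment starts. It can remove only patients who cannot be responders, so any error it causes is in the favourable direction.

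The SAP avoids this for radiological response. Its Response-Evaluable population in SAP 3.7.2 admits patients who "have died within 105 days of receiving their first dose, or" who clinically progressed in the same period, and SAP 5.1.2 treats patients without a post-baseline RECIST assessment as non-responders. The CA-125 set has no equivalent provision.

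At stake is the percentage in a table that will be read as a response rate by the GCIG criteria, although its denominator is not the one those criteria prescribe as the protocol reproduces them. The missing interference rule is a second departure from the same appendix and needs separate treatment.

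**Working it through.** The documents state no CA-125 response rate, no number with a qualifying baseline and no missing fraction, so there is no figure of the plan's own to reproduce. The size below is conditional on assumed inputs.

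**1. Effect of the post-dose condition.** Let N be the dosed patients with baseline at least 2×ULN, M those of them with no post-dose CA-125, R the responders, and m = M/N. None of the M patients can be among the R.

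- Appendix F rate: R/N
- SAP rate: R/(N − M) = (R/N)/(1 − m)

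The ratio 1/(1 − m) is never below 1. It exceeds 1 as soon as one patient lacks a sample, and the percentage then rises if there is at least one responder.

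Take N = 40, the planned size of Cohorts 1 and 5, as if all had a qualifying baseline (an assumption), and R = 16, an assumed 40% rate:

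| Assumed m | M | SAP rate |
|---|---|---|
| 0 | 0 | 16/40 = 40.0% |
| 5% | 2 | 16/38 = 42.1% |
| 10% | 4 | 16/36 = 44.4% |
| 15% | 6 | 16/34 = 47.1% |

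The ratio does not depend on N or on the true rate. With an intent-to-treat rate anywhere from 20% to 50%, m = 5% adds 1.1 points (20/0.95 = 21.1) to 2.6 points (50/0.95 = 52.6), and m = 10% adds 2.2 points (20/0.90 = 22.2) to 5.6 points (50/0.90 = 55.6).

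**2. What limits m.** On Schedule A, CA-125 is drawn with imaging every 6 weeks ± 1 (protocol 10.5 and Appendix A). It is also listed at the End of Treatment visit (10.7) and at the 28-day follow-up (10.8). A patient who stops early and attends these visits should have a value. The patients without one would mainly be early deaths, withdrawals from follow-up and missed visits.

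**3. Effect of omitting the interference rule.** Suppose k patients in a set of n had interference and r of them responded. Excluding them changes the rate from R/n to (R − r)/(n − k). The rate falls if r/k is above R/n and rises if it is below. Nothing in the documents says which applies.

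Assume N = 32, M = 2 and R = 12:

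- SAP set: 12/30 = 40.0%
- Intent-to-treat denominator only: 12/32 = 37.5%
- Intent-to-treat, also excluding 3 interference patients, none a responder: 12/29 = 41.4%
- The same, all 3 responders: 9/29 = 31.0%

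**4. Why the interference rule is a live question here.** Cohort 3 requires a biopsy at Cycle 2 Day 8 ± 3. With 21-day cycles and no delay, that is study day 29 ± 3, or 26 to 32. The first scheduled on-treatment CA-125, at 6 weeks ± 1, falls at about day 35 to 49. The gap is therefore 35 − 32 = 3 to 49 − 26 = 23 days, always inside 28. Whether such a biopsy counts as interference when the site is peritoneal or pleural is not stated.

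**The case against.** The strongest reply is that little depends on this. The endpoint as listed is a number of patients, and the post-dose condition leaves that number untouched. There is no formal hypothesis test. Appendix E bars the use of CA-125 alone to assess response or progression, and ORR, PFS and TTP do not use this population. CA-125 results, derived responses and procedures are all listed, so a reader of the study report could recompute the rate. All of this stands, and it limits the consequence. It does not justify the denominator: SAP 3.8 reports categorical outcomes as number and percent, and the percentage is the part affected.

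A reader might infer that both departures inflate the rate, because a fall in CA-125 after drainage could be scored as a drug response. The documents do not support that. The mechanism is possible, but omitting the rule raises the rate only if the affected patients respond more often than the rest, and step 3 shows the combined correction moving the percentage either way. Inclusion criterion 6 also requires major surgery to be completed four weeks before Day 1. That covers part of the pre-baseline interference, though not biopsies or procedures on treatment.

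A reader might also take 44% to 47% as the likely result. That range assumes 10% to 15% without a sample. It would rest on the six-week draw alone, while the End of Treatment and follow-up draws could bring m close to zero.

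Finally, Appendix F pulls two ways. Its intent-to-treat sentence, read literally, makes every patient with a qualifying baseline evaluable; its interference sentence makes some of them not evaluable. It also does not say whether the 28 days run back from baseline or from any sample. The SAP cannot simply be told to follow Appendix F without settling this.

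**Conclusion.** The contradiction between SAP 3.7.3 and Appendix F on the denominator is established, and its bias runs one way: the reported percentage is the intent-to-treat rate times 1/(1 − m). The size is unknown because m is not given. It is nil at m = 0 and, for an assumed 40% rate, 2.1 points at 5%, 4.4 at 10% and 7.1 at 15%. The responder count is unaffected.

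The omission of the interference rule is also established, but its effect has no known direction, and neither does the net effect of both departures.

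This is a descriptive secondary endpoint, so alpha, power and sample size are not involved. The change should be made before database lock, up to which point SAP 1.1 allows modification.

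**What to change.** In SAP 3.7.3, define the main CA-125 denominator as all dosed expansion-cohort patients with a baseline CA-125 of at least 2×ULN taken within two weeks before treatment. Count those with no post-dose sample as non-responders. Keep the present set as a sensitivity analysis, and report the number excluded from it so that m is visible.

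In SAP 5.1.7, state how Appendix F's interference sentence combines with its intent-to-treat sentence:

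- whether affected patients leave the denominator or stay in it as non-responders;
- whether the 28 days are counted from baseline or from each sample;
- whether the Cohort 3 Cycle 2 biopsy counts as interference.

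Apply the rule from the procedure records that SAP 6.9 already requires, and say in the same place how Appendix F's mouse-antibody condition is handled.

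The cost is a few sentences of SAP text, one additional analysis and, if any patient lacks a post-dose sample, a slightly less favourable percentage from the denominator change. No new data are needed.
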